#### 7.4.4.1. Statistical Methodology Specification

Endpoint

 
Rate of HES flares.
 

Model Specification

 
Wilcoxon Rank Sum test stratified by baseline OCS dose (0-≤20mg/day and >20mg/day prednisone or equivalent) and region.
 
Supplemented by an analysis using a negative binomial generalised linear model with a log-link function, including terms for baseline OCS dose (continuous scale), region and treatment, and including the log of the observed time as an offset variable. The model estimated mean flare rate per year will be weighted according to the observed proportion of the categorical covariates in the study data by inclusion of the OM (obsmargins) option in the LSMEANS statement of the GENMOD procedure. Missing data will be assumed to be missing at random (MAR) in this analysis.
 

Model Checking & Diagnostics

 
The fit of the negative binomial generalised linear model will be investigated by calculating and plotting standardised deviance residuals.
 

Model Results Presentation

 
In each treatment group: 
 
Median rate/year. 
 
Median rate/year for HES flares meeting definition a) (see Section 7.1.1).
 
Median rate/year for HES flares meeting definition b) (see Section 7.1.1).
 
 
 
Adjusted mean rate/year from negative binomial model.
 
 
 
p-value for difference between treatments in rate/year from Wilcoxon Rank Sum test.
 
Rate ratio and 95% CI from negative binomial model.
 
p-value from negative binomial model.
 

Subgroup Analyses

 
No subgroup analyses will be performed on this endpoint.
 

Sensitivity and Supportive Statistical Analyses

 
In order to assess the impact of missing data, a sensitivity analysis using a negative binomial generalized linear model will be performed using the ITT population. Missing data for subjects withdrawing from the study prematurely will be imputed for the period between withdrawal from the study and Week 32. For subjects in the mepolizumab treatment group, the missing time period will be imputed assuming that the subject's expected flare rate is shifted to that of the placebo arm (Jump to Reference [J2R]) [Keene, 2014]. For subjects in the placebo group, missing data will be assumed MAR.
 

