7.2. Screening and Critical Baseline Assessments

Cardiovascular medical history/risk factors (as detailed in the CRF) will be assessed at screening.

The following demographic parameters will be captured: year of birth, sex, race and ethnicity.

Medical/medication history will be assessed as related to the inclusion/exclusion criteria listed in Section 5.

Procedures conducted as part of the subject's routine clinical management [e.g., blood count] and obtained prior to signing of informed consent may be utilized for screening or baseline purposes provided the procedure meets the protocol-defined criteria and has been performed within the timeframe defined in the Time and Events Schedule.

PRO questionnaires should be completed by subjects before any other assessment at a clinic visit.

Evaluation of medical history relating to the subject's HES at screening includes:

- Date of diagnosis and/or approximate duration since diagnosis
- Requirement for therapy (e.g., immunosuppressive or cytotoxic therapy) including OCS for the management of their HES during 12 months prior to screening (Visit 1)
- Number and type(s) of HES flares (including organ systems affected and the type of interventions) experienced during the 12 months prior to screening (Visit 1). Refer to Section 5.1 for the definition of a historical HES flare (Inclusion Criterion #4).
- Documentation of any of the following complications of HES: gangrene, massive pulmonary hemorrhage or respiratory failure requiring ventilator support, congestive cardiac failure, renal failure requiring dialysis, cerebrovascular accident.

At randomization (Visit 2), the HES Core Assessments will be completed to establish the baseline characteristics of subjects' HES. Throughout the treatment period, the same set of the assessments will be utilized to monitor changes in their disease activity for major organ systems affected by HES. Further information can be found in Section 7.3.2.

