9.2. Sample Size Considerations

9.2.1. Sample Size Assumptions

This study is designed to test the superiority of mepolizumab versus placebo.

The primary efficacy endpoint is the proportion of subjects who experience an HES flare during the 32-week study treatment period. The power calculation assumes that 60% of subjects on placebo will experience an HES flare during the 32-week study treatment period. With a two-sided 5% level of significance and a sample size of 40 randomized subjects per arm, the null hypothesis will be rejected if the observed proportion of patients with an HES flare on placebo is 60% and on mepolizumab is 35% or less. If the true population proportion of subjects who would experience an HES flare during the 32-week study treatment period on placebo is 60% and on mepolizumab is 22%, the study has 90% power for demonstrating a statistically significant result for this assumed true population effect.

This endpoint is novel, and has not explicitly been used in clinical trials of HES. There is therefore little previous data on which to base estimates of the number of subjects who will experience an HES flare during the 32-week study treatment period.

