## 5.4. Examination of Covariates, Other Strata and Subgroups

### 5.4.1. Covariates and Other Strata

- Region and baseline OCS dose, expressed as prednisone equivalent dose, will be covariates in all statistical analysis. These covariates will be included as stratification variables for the Cochran-Mantel-Haenszel test and Wilcoxon Rank Sum test according to the table below. For parametric analysis models, region will be included as a fixed categorical effect and baseline OCS dose will be included as a fixed continuous effect.

Category	Covariates and / or Subgroups
Region	See Section 5.3. 
 
USA
 
Argentina, Mexico and Brazil
 
Rest of World
 

Baseline oral prednisone equivalent dose 	See Section 5.4.1.1 
 
0-≤20mg prednisone or equivalent
 
>20mg prednisone or equivalent
 

For parametric analysis models, baseline OCS dose will be included as a fixed continuous effect.

- If the percentage of subjects is small within a region, then the region categories may be refined prior to unblinding the trial.
- For analyses where a baseline value of the analysis variable is available this will also be included in the statistical analysis. These covariates will be included as stratification variables for the Cochran-Mantel-Haenszel test and Wilcoxon Rank Sum test, and as continuous fixed effects for all parametric analysis models.

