### 7.1.4.1. Statistical Methodology Specification

Primary Statistical Analyses
Endpoint

 
Proportion of subjects who experience a HES flare during the 32-week study treatment period.
 

Model Specification

 
Cochran-Mantel-Haenszel test stratified by baseline OCS dose (0-≤20mg/day and >20mg/day prednisone or equivalent) and region.
 
Supplemented by a logistic regression analysis adjusting for covariates of baseline OCS dose (continuous scale), region, and treatment.
 

Model Checking & Diagnostics

 
To examine the fit of the logistic regression model, deviance residuals will be calculated and plotted.
 

Model Results Presentation

 
Number of subjects analysed in each treatment group.
 
Number of subjects with ≥1 HES flare or who withdraw from the study prior to Week 32 (Visit 11). 
 
Number of subjects with ≥1 HES flare.
 
Number of subjects with no HES flare who withdraw from the study prior to Week 32 (Visit 11).
 
 
 
Number of subjects with no HES flare who complete Week 32 (Visit 11).
 
p-value from Cochran-Mantel-Haenszel test.
 
Odds ratio and 95% Confidence Interval (CI) from logistic regression model.
 
p-value from logistic regression model.
 

Subgroup Analyses

 
A logistic regression analysis will be fitted separately within each subgroup of interest defined in Section 5.4.2.
 
Odds ratios and 95% confidence intervals from the logistic regression model will be presented. Analysis will be descriptive only; no p-values will be presented for the subgroup analyses. If the number of subjects in each subgroup category are small, confidence intervals may also be omitted.
 

Sensitivity and Supportive Statistical Analyses

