#### 7.2.4.1. Statistical Methodology Specification

Endpoint

 
Time to first HES flare.
 

Model Specification

 
Log-rank test stratified by baseline OCS dose (<math>0 \leq 20</math>mg/day and <math>>20</math>mg/day prednisone or equivalent) and region.
 
Supplemented by a Cox proportional hazards regression model allowing for covariates of baseline OCS dose (continuous scale) and region.
 

Model Checking & Diagnostics

 
To examine the fit of the Cox proportional hazards model, martingale and deviance residuals will be calculated and plotted.
 

Model Results Presentation

 
In each treatment group             
 
Number of subject analysed.
 
Number of subjects with HES flare.
 
 
 

- Number of subjects censored at study withdrawal.
- Number of subjects censored at study completion.
- Stratified Log-Rank test p-value for association between treatment and time to first HES flare.
- Hazard ratio and 95% CI from Cox proportional hazards model.
- Wald chi-square p-value from Cox proportional hazards model.

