### 9.3.2. Investigation of Covariates

The impact of the following prospectively selected covariates on mepolizumab exposure (e.g. clearance) will be evaluated using the procedures described in Section 9.3.3.

Category	Covariates
Demographics	Weight (included in the structural model), age, race, gender, country
Baseline clinical status	Creatinine clearance, albumin (both already included in the

Category	Covariates
	current model), serum creatinine, alanine aminotransferase, aspartate aminotransferase, alkaline phosphatase, bilirubin, total protein
Baseline disease status	Flare history, blood eosinophils and baseline OCS dose
Concomitant medications	If data permits*, e.g. immunosuppressant therapies (e.g. methotrexate, azathioprine and mycophenolate mofetil), proton pump inhibitors, statins, pain relief (e.g. paracetamol, NSAIDs), interferon alfa and antihypertensive drugs
Others	Presence/absence of anti-drug antibodies and previous biologics use (monoclonal antibodies).

\*Attempt to investigate those classes of drug will be made providing data permits.

Covariate selection will be based on physiological plausibility, supported by graphical evaluation (PK parameters vs. covariates), and formally by automated linear model fitting using proc glmselect in SAS 9.2 (or higher). Individual PK parameters and covariates will be log-transformed and standardized before analysis. For forward and backward selections, significance levels of 0.1 and 0.05 will be applied respectively, in line with criteria used in previous analyses. Co-linearity between covariates will be carefully considered.

Identified covariates will then be subjected to traditional covariate analysis (with estimation step) and will follow the procedures described in Section 9.3.3. If deemed appropriate box plots of systemic clearance versus covariates of interest (e.g., immunogenicity status) will be provided.

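### The negative binomial model for the rate of HES flares omits the prior-year flare count, a baseline predictor already collected that could modestly sharpen the rate ratio at almost no cost

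*SAP*

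**What the plan says.** Protocol 7.2 lists, among the HES history taken at screening, "Number and type(s) of HES flares (including organ systems affected and the type of interventions) experienced during the 12 months prior to screening". Inclusion criterion 4 (Protocol 5.1) requires at least two such flares, so every eligible subject has a count of two or more.

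SAP 7.4.4.1 tests the flare rate with a Wilcoxon rank sum test stratified by baseline OCS dose and region. It supplements this with a negative binomial model, "including terms for baseline OCS dose (continuous scale), region and treatment, and including the log of the observed time as an offset variable". The rate ratio, its 95% confidence interval and the adjusted mean rates all come from that model. A jump-to-reference (J2R) version serves as the missing-data sensitivity analysis. Protocol 9.4.1 names the same terms for the rate model: treatment, region, baseline OCS dose and a time offset.

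The other flare endpoints follow the same pattern. For the primary endpoint: "Supplemented by a logistic regression analysis adjusting for covariates of baseline OCS dose (continuous scale), region, and treatment". For time to first flare: "Supplemented by a Cox proportional hazards regression model allowing for covariates of baseline OCS dose (continuous scale) and region".

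Prior flares appear as a covariate only in pharmacology modelling. The baseline disease status row of SAP 9.3.2 reads "Flare history, blood eosinophils and baseline OCS dose", and SAP 13.3.2 has a similar entry.

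**The concern.** For a recurrent-event endpoint, a subject's own recent event count is usually the first covariate one would consider. Here it is collected for everyone, is fixed before randomisation and costs nothing to use. If subjects who flared often last year tend to flare often on study, part of the between-subject variation that widens the rate-ratio interval can be explained.

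Randomisation is stratified by region only (Protocol 6.2). With about 80 subjects, flare history is balanced by chance alone, and the negative binomial model would not correct an imbalance. What is at stake is the width of one confidence interval and some protection against chance imbalance. The validity of the comparison is not in question.

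**Working it through.** **1. The plan's own figure.** The documents give no power, dispersion or precision for the rate ratio. The only design figure concerns the primary endpoint (Protocol 9.2.1): "With a two-sided 5% level of significance and a sample size of 40 randomized subjects per arm", and, for true flare proportions, "on placebo is 60% and on mepolizumab is 22%, the study has 90% power". It reproduces:
- Fisher's exact test with 40 per arm, 60% against 22%, has power 91.9%.
- The continuity-corrected formula needs 39 per arm.
- For the stated rejection limit, 24/40 against 14/40 (35%) gives p = 0.043, and 24/40 against 15/40 gives p = 0.073.

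These flare proportions are therefore a fair anchor for event rates.

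**2. Formula for the rate ratio.** With n = 40 per arm, mean counts m0 and m1 and dispersion k:

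Var(log RR) = (1/m0 + 1/m1 + 2k) / 40

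Only the 2k term can shrink when a covariate explains between-subject variation. The means are set so that P(at least one flare) is 60% and 22%: m0 = (0.40^(-k) - 1)/k and m1 = (0.78^(-k) - 1)/k. For k = 1, m0 = 1.5 and m1 = 0.282, so Var = (0.667 + 3.546 + 2)/40 = 6.212/40 and SE = 0.394. The dispersion share is 2/6.212 = 32%. If the count explained half of it, the variance would fall by 16% and the SE to 0.361.

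| k (assumed) | SE now | Dispersion share of variance | Fall in variance if 10% / 25% / 50% of k is explained |
|---|---|---|---|
| 0.5 | 0.376 | 18% | 2% / 4% / 9% |
| 1 | 0.394 | 32% | 3% / 8% / 16% |
| 1.43 (= 1/0.7) | 0.410 | 42% | 4% / 11% / 21% |
| 2 | 0.433 | 53% | 5% / 13% / 27% |

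If nothing is explained, the fall is zero.

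**3. Simulation, one shared patient effect.** Inputs: 40 per arm; Poisson flares with a gamma patient effect (assumed shape 0.7 to 2, that is k = 1.43 to 0.5) driving both past and on-study flares; prior count of 2 or more enforced; true rate ratio 0.5; log(prior count) added to the model.

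| Shape | Ratio of squared median SEs, with / without | Fall in variance | Power without, with |
|---|---|---|---|
| 0.7 | 0.79 | 21% | 72%, 82% |
| 1 | 0.87 | 13% | 76%, 82% |
| 2 | 0.95 | 5% | unchanged at 75-76% |

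The power is that of the negative binomial model, not of the confirmatory test. Repeat runs under the same structure gave falls of 3% to 19%. A set with the mean prior rate before truncation set to 1 or 2 per year spanned 1% to 27% model-based (2% to 22% empirical).

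**4. Simulation, weaker link.** With 60% sharing of the patient effect, one set gave falls of 2% to 8% and another 0% to 10%; empirical variance in the latter ran from +3% to -7%. With no link the fall was 0%.

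**5. Simulation, cautious end.** Inputs: on-study flare proportions of 60% and 22%; past and on-study patient effects correlated from 0 to 0.99; assumed k from 0.5 to 2; mean prior rate 2 per year before truncation; dispersion held fixed in the fit. The empirical SE changed by +0.9% to -2.6%, or +1.8% to -5.1% in variance (1.009^2 and 0.974^2). With zero correlation the SE changes were +0.3%, +0.1% and +0.9%, so an uninformative covariate costs almost nothing.

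**6. Why the simulations differ.** At 22% flaring on mepolizumab, 1/m1 dominates the variance. With k = 1 and m0 = 1.5, moving the rate ratio from 0.188 (m1 = 0.282) to 0.5 (m1 = 0.75) raises the dispersion share from 32% to 2/(0.667 + 1.333 + 2) = 50%, so there is more to gain. Holding the dispersion fixed in step 5 also keeps the adjusted fit from benefiting from a smaller residual dispersion.

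**7. Logistic model.** With the step 3 structure and a mean prior rate of 2 per year, the median SE of the log odds ratio rose from 0.459 to 0.496, 0.459 to 0.490 and 0.466 to 0.482 (shape 0.7, 1, 2), 3% to 8% larger. A further set gave rises of 1% to 8%, with power changing by -2 to +2 points. The Cox model was not simulated.

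**The case against.** The covariate set is deliberate and consistent between protocol and SAP, and the model only supplements a rank test whose p-value enters the hierarchy. Nothing confirmatory changes. The link to on-study flares may also be weak. A historical flare is any documented escalation for symptoms or eosinophil counts (Protocol 5.1). An on-study flare needs an OCS increase of at least 10 mg/day for 5 days, a cytotoxic or immunosuppressive increase, or two blinded active OCS courses (SAP 7.1.1). The windows differ, 12 months against 32 weeks, and the entry minimum of two truncates the count. All of this stands. It limits the size of the gain but gives no reason to leave the count out.

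A reader might infer that the SAP breaks its own rule in 5.4.1: "For analyses where a baseline value of the analysis variable is available this will also be included in the statistical analysis". The documents do not support that. SAP 5.2 defines no baseline for flares; its general definition is the latest assessment before first dose, and the historical count is a differently defined variable. The rule would also require such a covariate to stratify the CMH and Wilcoxon tests, so it cannot be invoked for the model alone. The pharmacology covariate lists show no inconsistency either: there, prior flares are one candidate among many for exposure or eosinophil response.

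A reader might also infer that the odds ratio and hazard ratio lose precision. For the odds ratio, step 7 shows the reverse: adjustment targets a different, conditional effect and can enlarge its SE. For the hazard ratio the claim is unsupported.

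**Conclusion.** The point holds for the negative binomial rate model: a plausible predictor, recorded for every subject, is left out of the model that produces the rate ratio and its interval. That much is certain from the documents.

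The size is not. A reasonable range for the fall in the variance of the log rate ratio is 0% (no link) to about 20% (one persistent patient effect, high dispersion). Only the most favourable assumptions reach 27%, and the cautious simulation stays within about 5%. All of these figures rest on assumed dispersion and an assumed past-to-on-study correlation. No scenario shows a material loss from including the term.

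This is a modest efficiency improvement to a supplementary estimate. It does not bias the randomised comparison, alter any confirmatory p-value, show a breach of the SAP's covariate rule or justify changing the main logistic and Cox models.

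**What to change.** Before unblinding:
- In SAP 7.4.4.1, add log(number of HES flares in the 12 months before screening) as a continuous covariate to the negative binomial model and to its J2R sensitivity analysis.
- Name the covariate in SAP 5.4.1, stating that it applies to the rate model only.
- List it in SAP 2.4 as a change from the covariates in Protocol 9.4.1, with the reason.
- Leave the CMH, log-rank and Wilcoxon tests unchanged. Any version of the logistic or Cox model adjusted for the count should be labelled supportive.

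The cost is one model term and a few lines of SAP text. The data are already collected.

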## **7.5. Secondary Efficacy Analysis – Change from Baseline in Fatigue Severity BFI Item 3 (Worst Level of Fatigue in Past 24 Hours) at Week 32**

### **7.5.1. Endpoint / Variables**

The BFI has 9 items. The subject rates their fatigue level right now, their usual fatigue level over the last 24 hours and their worst level of fatigue over the last 24 hours using an 11-point rating scale anchored at 0 (no fatigue) and 10 (as bad as you can imagine). The subject also rates how, during the past 24 hours, fatigue has influenced each of the following on an 11-point rating scale anchored at 0 (does not interfere) and 10 (completely interferes): general activity, mood, walking ability, normal work, relations with other people and enjoyment of life. The subject completes item 3 (worst level of fatigue during past 24 hours) of the BFI daily and the full BFI every 7 days at home on the eDiary.

The change from baseline in fatigue severity (worst level of fatigue during past 24 hours) at Week 32 will be calculated using the mean of the 7 daily assessments of BFI item 3 up to and including the date of the Week 32 visit as the Week 32 assessment, and the mean of the 7 daily assessments of BFI item 3 up to but not including the date of first dose of study treatment as the baseline assessment. If any of the 7 daily assessments of BFI item 3 are missing for either the Week 32 time point or the baseline time point, the mean of the available daily assessments over the 7-day period will be used to calculate the change from baseline.

### **7.5.2. Summary Measure**

The difference between mepolizumab and placebo in the change from baseline BFI item 3 at Week 32.

### **7.5.3. Strategy for Intercurrent (Post-Randomization) Events**

The treatment effect to be estimated (estimand) will be the ‘treatment policy’ effect of initial randomised treatment. A treatment policy strategy will be used for the intercurrent events of a) discontinuation of study medication and b) receipt of alternative HES medications. Subjects with missing change from baseline BFI item 3 at Week 32 will be included in the analysis with the largest (i.e. worst) value observed for any subject. Sensitivity analyses to assess the impact of missing data will be performed.

### **7.5.4. Statistical Analyses / Methods**

Details of the planned displays are provided in [Appendix 10](#): List of Data Displays and will be based on GSK data standards and statistical principles.

Summary statistics for BFI item 3 at each week of treatment will be presented, including change from baseline values. Assessment windows for each week are defined in [Section 16.3.1](#).

The clinical relevance of changes in BFI item 3 at Week 32 will be assessed using a cumulative distribution plot showing the percentage of subjects in each treatment group with a reduction in BFI item 3 greater than equal to each value in the observed range; this will allow assessment of the treatment difference against a range of clinically important differences.

Endpoint

 
Change from baseline in fatigue severity (BFI item 3) at Week 32.
 

Model Specification

 
Wilcoxon Rank Sum test stratified by baseline fatigue severity (“severe” defined as BFI item 3 <math>\geq 7</math>, and “not severe” defined as BFI item 3 <math>< 7</math>), baseline OCS dose (<math>0 \leq 20</math>mg/day and <math>> 20</math>mg/day prednisone or equivalent) and region. This will be implemented using the FREQ procedure with the SCORES = MODRIDIT option.
 

Model Checking & Diagnostics

 
Not applicable.
 

Model Results Presentation

 
Number analysed in each treatment group.
 
Median change from baseline BFI item 3 at Week 32 in each treatment group.
 
p-value for difference between treatments from Wilcoxon Rank Sum test.
 

Subgroup Analyses

 
No subgroup analyses will be performed on this endpoint.
 

Sensitivity and Supportive Statistical Analyses

 
Repeated measures analysis including assessments at Week 4, 8, 12, 16, 20, 24, 28 and 32. In this analysis missing data will be assumed to be missing at random and will not be imputed with the largest i.e. worst value. A mixed effects model will be fitted with the following specification: 
 
Time point, treatment and region included as fixed categorical effects.
 
Baseline BFI and baseline OCS dose included as continuous fixed covariates.
 
Interaction terms for baseline-by-timepoint and treatment-by-time point interaction.
 
The Kenward and Roger method (DDFM = KR) for approximating the denominator degrees of freedom to correct for bias in the estimated variance-covariance matrix.
 
REPEATED statement with TYPE=UN to specify an unstructured covariance structure for the R matrix.
 
The OBSMARGIN option on the LSMEANS statement in order to compute the adjusted geometric means with weights proportional to the input data set.
 
 
 

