9.2.3. Sample Size Re-estimation or Adjustment

While the estimate of 60% of placebo subjects and 22% of mepolizumab subjects having an HES flare during the 32-week study treatment period is felt by clinical experts to be reasonable for this population, the proportion of subjects who have an HES flare will be monitored, blinded to treatment, and if the blinded overall proportion is predicted to be <30% the sample size may be increased up to a maximum of 60 subjects per group (total 120 subjects). The planned increase to sample size will depend on the observed blinded overall proportion of subjects as follows:

Blinded overall proportion ¹ (%)	N per group
≥30	40 (no increase)
27.5 – 30	45
25-<27.5	50
<25	60

¹Proportion of subjects who have an HES flare during the 32-week study treatment period.

The decision to increase the sample size will be made when at least 30 subjects per arm have been randomised. The blinded overall proportion of subjects who have an HES flare will be calculated based on the HES flare data available in the CRF. This will include all HES flares meeting flare endpoint definition ‘a)’ in Section 7.3.1. The number of HES flares due to flare endpoint definition ‘b)’ is expected to be small, therefore in order to maintain the blood eosinophil blinding, HES flares due to subjects receiving two or more courses of blinded active OCS will not be included in the calculation of the blinded overall proportion.

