The change from baseline in fatigue severity at week 32 will be compared between treatment groups using a stratified Wilcoxon Rank Sum test, stratified by baseline fatigue severity (“severe” defined as BFI item 3 ≥ 7 , and “not severe” defined as BFI item 3 < 7) and region.

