### 2.3. Statistical Hypotheses / Statistical Analyses

The primary efficacy endpoint is the proportion of subjects who experience a HES flare during the 32-week study treatment period. This study is designed to test the superiority of mepolizumab versus placebo. The primary analysis will test the following hypothesis:

- **Null hypothesis:** no difference between mepolizumab relative to placebo for the proportion of subjects who experience a HES flare during the 32-week study treatment period.
- **Alternative hypothesis:** the proportion of subjects who experience a HES flare during the 32-week study treatment period is smaller for mepolizumab compared to placebo.

Significance tests will be performed at the two-sided 5% level (one sided 2.5%).

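### Beyond the change score itself, the confirmatory BFI item 3 test adjusts for baseline fatigue only by a cut at 7; a rank ANCOVA on the full baseline would add some power at no cost in patients

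*SAP*

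**What the plan says.** - SAP 5.5 places change from baseline in BFI item 3 at Week 32 fifth and last in the fixed testing sequence.
- SAP 7.5.1 defines both the baseline and the Week 32 value as the average of up to 7 daily scores on a 0 to 10 scale.
- SAP 7.5.3 gives subjects with no Week 32 change the worst change seen in any subject.
- SAP 7.5.4 specifies a "Wilcoxon Rank Sum test stratified by baseline fatigue severity", where severe means a baseline of at least 7. Baseline OCS dose (2 levels) and region (3 levels) are further strata, and modified ridit scores are used. That makes 2 × 2 × 3 = 12 strata.
- Protocol 9.4.1 has the same cut ("stratified by baseline fatigue severity"), with region but without OCS dose.
- SAP 5.4.1 sets the general rule: the baseline of the analysed variable enters rank tests as a stratum, "and as continuous fixed effects for all parametric analysis models".
- The supportive repeated-measures model in SAP 7.5.4 follows that rule: "Baseline BFI and baseline OCS dose included as continuous fixed covariates".
- Protocol 9.2.1 rests on "a sample size of 40 randomized subjects per arm" and gives power for the flare endpoint only. No BFI effect, SD, correlation, missing share or power is stated.

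**The concern.** A 7-day mean is close to continuous, and cutting it at 7 discards most of its detail. In the lower stratum a subject who starts at 1 is ranked directly against one who starts at 6.5, although the second has far more room to improve. If baseline and Week 32 have equal SDs and correlation r, the slope of change on baseline is −(1 − r). At r = 0.3, each extra point at baseline goes with 0.7 points more fall, whatever the treatment. If baseline had mean 4.5 and SD 2.5, the cut would lie at (7 − 4.5)/2.5 = 1 SD, and about 84% of subjects would share the lower stratum. The baseline-driven spread within that stratum stays in the ranks as noise, and a chance baseline imbalance within it is not corrected.

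This is the only patient-reported endpoint in the hierarchy. The trial is small and was not powered for it, so power lost here could decide whether a fatigue claim is supported.

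**Working it through.** **1. The plan's own figure.** Protocol 9.2.1 states that if the true flare proportion "on placebo is 60% and on mepolizumab is 22%, the study has 90% power". The two-proportion formula with pooled null variance, two-sided 5%, gives n = (1.96·√(2·0.41·0.59) + 1.2816·√(0.60·0.40 + 0.22·0.78))² / 0.38² = 33.1, so 34 per arm. With the continuity correction this becomes 39 per arm, against 40 planned. Exact power at 40 per arm is 91.9% (Fisher). The figure reproduces, but it concerns flares only.

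**2. Assumed inputs for BFI item 3.** 40 per arm; baseline mean 4.5 to 6.5, SD 2 to 2.5, scores clipped to 0–10 in the simulations; correlation r from 0.2 to 0.9; 0 to 15% missing. None of these BFI values is in the documents.

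**3. The cut alone, by normal approximation.** This ignores strata, clipping and missing data.
- Share of baseline variance captured by the cut: R² = φ(c)² / [Φ(c)(1 − Φ(c))], with c = (7 − mean)/SD. For 4.5 (2.5), c = 1 and R² = 0.2420²/(0.8413 × 0.1587) = 0.44.
- Variance of change given continuous baseline: SD²(1 − r²). At r = 0.3: 6.25 × 0.91 = 5.69.
- Variance of change given the cut: SD²[(1 − r²) + (1 − r)²(1 − R²)]. At r = 0.3: 6.25 × (0.91 + 0.49 × 0.56) = 7.41.
- A shift of √5.69 × 2.8 × √(2/40) = 1.49 gives 80% power with continuous baseline. With the cut, 1.49/(√7.41 × √(2/40)) = 2.45, and Φ(2.45 − 1.96) gives 68.9%.

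Against 80% with continuous baseline, the cut gives:

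| Mean (SD) | r = 0.3 | r = 0.5 | r = 0.7 |
|---|---|---|---|
| 4.5 (2.5) | 68.9% | 72.9% | 76.1% |
| 6 (2) | 71.5% | 74.6% | 77.1% |

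The loss is about 3 to 11 points.

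**4. Simulation of the planned test.** Modified ridit scores, 40 per arm, missing set to the worst observed change, shift set as in step 3. Power in %:

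| Mean (SD), r | Missing | Planned, 12 strata with cut | 12 strata plus continuous baseline | Rank ANCOVA, 6 strata |
|---|---|---|---|---|
| 4.5 (2.5), 0.3 | 0 | 56.4 | 63.9 | 66.6 |
| 4.5 (2.5), 0.3 | 8% | 41.6 | 47.2 | 49.7 |
| 4.5 (2.5), 0.7 | 0 | 63.5 | 66.8 | 69.3 |
| 4.5 (2.5), 0.7 | 8% | 47.5 | 49.0 | 52.5 |
| 6 (2), 0.3 | 0 | 58.8 | 64.1 | 69.0 |
| 6 (2), 0.3 | 8% | 45.6 | 49.3 | 51.1 |
| 6 (2), 0.7 | 0 | 61.7 | 62.8 | 69.3 |
| 6 (2), 0.7 | 8% | 49.6 | 49.3 | 52.7 |

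With 1,000 to 1,500 runs per setting, each figure has a standard error of up to √(0.25/1000) = 1.6 points. Under the null, the planned test rejected in 5.0% of trials and the rank ANCOVA in 4.4%.

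**5. Splitting the gain.** In the first row, 63.9 − 56.4 = 7.5 points come from the continuous baseline and 66.6 − 63.9 = 2.7 from fewer strata. In the seventh row the split is 1.1 and 6.5. Removing the cut and putting nothing in its place changes power by −5.4 to +1.7 points over these rows, so fewer strata without baseline adjustment do not explain the gain.

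**6. Wider range.**
- Taking residuals of change on continuous baseline, giving missing subjects the worst residual and testing in 6 strata gains about 5 to 15 points at r = 0.3 to 0.7, and 3 to 7 at r = 0.85.
- The same adjustment with the 12 strata kept gains about 2 to 11 points, and 0 to 3 at r = 0.85.
- Rank ANCOVA with missing left at the worst observed change gains about 3 to 12 points.
- With 15% missing, the rank ANCOVA gain falls to 0.7 to 2.9 points.

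**The case against.** The choice is pre-specified in the protocol, follows one consistent rule in SAP 5.4.1, and keeps type I error. Nothing in the plan is wrong; this is a matter of efficiency. That stands, and it limits how hard the point can be pressed.

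Baseline is not ignored either. The change score subtracts it with a coefficient of 1, and the repeated-measures analysis uses it in full. That analysis cannot decide significance, though, and it assumes data missing at random instead of applying the worst-value rule. Its use of continuous baseline therefore shows that the covariate is available, not that the same model would suit the confirmatory test.

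A reader might infer that the cut by itself costs 5 to 16 points of power. The documents do not support that. They give none of the inputs, and a comparison of 12 strata with 6 mixes two changes. Keeping the cut as a regression term and moving to 6 strata already gains about 2.5 to 5 points.

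Giving missing subjects the worst residual would also depart from SAP 7.5.3, which assigns the worst change. That objection is met by leaving missing subjects at the worst observed change.

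**Conclusion.** The point holds as a modest, conditional loss of efficiency. For 40 per arm, correlation 0.3 to 0.85 and 0 to 10% missing, continuous baseline adjustment in the 6 OCS-by-region strata gains about 3 to 15 points of power, with type I error near 5%. The continuous baseline with the 12 strata held fixed accounts for about 0 to 11 points, least at high correlation; the remainder is due to fewer strata. The direction is well supported, but the size cannot be derived from the documents and shrinks further if more data are missing. It would be wrong to conclude that the planned test is invalid or that fatigue at baseline goes unadjusted. The change is worth making because it is cheap. It affects a claim only if the four tests ahead of BFI item 3 all succeed.

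**What to change.** Before unblinding, amend SAP 7.5.4 to replace the severity stratum with a rank ANCOVA:

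1. Set missing change to the worst observed change, as SAP 7.5.3 states.
2. Rank change and rank baseline BFI item 3.
3. Regress the change ranks on the baseline ranks, pooled over arms and without treatment, and keep the residuals.
4. Run the same modified-ridit test on the residuals, stratified by OCS dose and region.

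Record the change in SAP 2.4 and note the exception to the rule in SAP 5.4.1. Keep median change and the severity split as descriptive displays. If the worst-residual variant is preferred, declare it as a change to the missing-data rule.

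The cost is SAP text and a short program, with no new data or patients. It does replace a protocol-defined confirmatory test, and the p-value would then refer to baseline-adjusted ranks while the table shows raw change; the SAP should say so.
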